
# 1 RESEARCH HYPOTHESIS

We hypothesize that Cana may be able to improve number and function of CD34+ endothelial progenitor cells. We also propose that this expected cardiovascular benefit is independent of HbA1C reduction.

In this proposed study we plan to recruit patients with type 2 diabetes, who are on any combination of the following anti-diabetic therapies: metformin (1-2 grams), insulin, GLP-1 agonists, a DPP-IV inhibitor, or sulfonylureas, but still remain inadequately controlled with HbA1C between 7.0% and 10% (both values inclusive), but not overtly out of control (> 10% of HbA1C).

Subjects will begin taking 100 mg of Cana or placebo after initial 4 weeks. Subjects will be withdrawn from the study if the medication or placebo is not tolerated.

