	
20. Active wounds or recent surgery within 3 months. 21. Untreated hyper/hypothyroidism
 
Additionally, patients who are active smokers, patients who are pregnant, nursing women, and post-menopausal women who are on estrogen hormone replacement therapy (not including oral contraceptives) will be excluded.
 
Detailed Inclusion / exclusion criteria are listed on pages 12-15 of the protocol.

Criteria for Evaluation: (Efficacy, safety, stopping rules, etc.)
	
Subjects will be phone screened to determine initial eligibility. If the phone-screening indicates possible eligibility, then the subjects will come to an in-person screening visit at week -2, then evaluated for end points at weeks 0, 8 and 16. Follow up phone call will be done 30 days after last dose of study drug to assess for adverse effects.
 
Study participation will be stopped for adverse effects at the discretion of the study investigator. Subjects may stop study participation at any time and for any reason.

Statistics:
	
The total sample size is requested, after accounting for attrition over the 16-week period, is 20 subjects per group or 40 subjects total. Sample size estimates were based on the effects of exercise on CD34+/KDR+ cells as described in the literature. The effect of a single session, as well as extended training, on healthy subjects or those with existing cardiovascular conditions appears to increase the CD34+/KDR+ cells.
 
This is a pilot study; as a result appropriate power calculation is not feasible. We however did conduct power analysis, which provided us with 73% power (see statistics section). A p-value of less than 0.05 will be considered statistically significant.

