### **DISCONTINUATION OF SUBJECTS FROM TREATMENT**

Subjects **MUST** discontinue from the investigational product (and non-investigational product at the discretion of the investigator) for any of the following reasons:

- Withdrawal of informed consent (subject's decision to withdraw for any reason)
- Any clinical adverse event, laboratory abnormality, or inter-current illness which, in the opinion of the investigator, indicates that continued participation in the study is not in the best interest of the subject.
- Patients who progress to stages 3 and beyond, post screening will be excluded
- Pregnancy
  - Pregnant patients will be advised to contact the investigator or study staff immediately if they suspect they might be pregnant (e.g. missed or late menstrual period) at any time during study participation.
- Loss of ability to freely provide consent through imprisonment or involuntary incarceration for treatment of either a psychiatric or physical illness (e.g. infectious disease).
- If hyperglycemia and ketoacidosis is suspected, promptly discontinue treatment with Canagliflozin
- **All subjects who discontinue should comply with protocol-specified follow-up procedures outlined before.** The only exception to this requirement is when a subject withdraws consent for all study procedures or loses the ability to consent freely (i.e., is imprisoned or involuntarily incarcerated for the treatment of either a psychiatric or physical illness). If a subject withdraws before completing the study, the reason for withdrawal must be documented appropriately.

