### **DATA ANALYSIS**

Digital data files will be stored in a protected limited-access folder on the MFA network. Only the Study Biostatistician and the PI will have direct access to the data once it is on this server. The data file will have random subject identifiers and will have no HIPAA identifiers.

The distributional assumptions of all measures will be examined. Means and standard deviations will be computed for continuous measures and proportions for categorical variables. Graphical representations of the mean group slopes and individual slopes will be generated and inspected.

Study groups will be compared to determine whether any imbalance between the groups on patient characteristics remain after randomization. If imbalance is evident, by inspection, all models will be adjusted for the unbalanced covariates. Change in outcome over time will be examined using a multilevel approach with linear mixed models (LMM). The longitudinal multilevel modeling approach will enable us to examine characteristics of within-person change, as well as between-group differences that may influence change. LMMs handle missing data more efficiently than traditional ANOVA designs. In the linear mixed models, the patient is considered a random effect and the outcome measured at specific time points is nested within patient. Time (week 0, 8, 16) will be modeled as a continuous variable in order to assess linear effects from 0 to 8 to 16 weeks. In order to determine whether there are non-linear time effects (e.g., rapid increase from 0 to 8 weeks followed by little change from 8 to 16 weeks; or initial decrease at 8 weeks followed by increase at 16 weeks, etc.) we will also need to include models in which time is defined as a class variable (with 0 as the reference group). Subsequent analyses will add study group and other patient characteristics as covariates. We are particularly interested in whether there is a significant interaction between study group and time, adjusting for other patient level covariates. A significant interaction would indicate that the slopes in outcome over time differ by study group. If the global test of interaction is significant, subsequent significance testing of the pair wise comparisons of group slopes group will be adjusted for multiple comparisons. The model also includes coefficients for the group-by-time interactions and random effects for patient and time.

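### The protocol removes drug-intolerant patients from the study in two places and keeps them in follow-up in a third, so outcome collection after stopping study drug is undefined

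*Combined protocol and SAP*

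**What the plan says.** Three places in the combined protocol and SAP deal with a patient who cannot tolerate study medication.

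- Section 1, Research Hypothesis: "Subjects will be withdrawn from the study if the medication or placebo is not tolerated".
- Protocol Synopsis, Criteria for Evaluation: "Study participation will be stopped for adverse effects at the discretion of the study investigator".
- Section 3, Discontinuation of Subjects from Treatment. This lists reasons for stopping the investigational product. One of them is a best-interest test, whose opening words are: "Any clinical adverse event, laboratory abnormality, or inter-current illness which, in the opinion of the investigator, indicates that continued participation in the study is not". The section then adds "All subjects who discontinue should comply with protocol-specified follow-up procedures outlined before" and limits the exemptions: "The only exception to this requirement is when a subject withdraws consent for all study procedures or loses the ability to consent freely".

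A fourth place matters for any repair. Section 5, Pregnancy, withdraws a pregnant subject from the study as well as from treatment, whereas the discontinuation section lists pregnancy among the reasons to stop the product.

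On outcomes, the Synopsis has patients "then evaluated for end points at weeks 0, 8 and 16", followed by a telephone call for adverse effects 30 days after the last dose. On missing data, Section 7 (Data Analysis) offers only this: "LMMs handle missing data more efficiently than traditional ANOVA designs".

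**The concern.** Stopping a drug and leaving a trial are different events. The first changes what the patient takes; the second ends measurement. Section 1 and the Synopsis merge them for intolerance and adverse effects, while the discontinuation section keeps the patient under follow-up. Staff who follow Section 1 would stop collecting outcomes from patients whom the discontinuation section still counts as being in follow-up.

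What is at stake is outcome data missing because of the treatment itself. A mixed model gives valid estimates when missingness depends only on data it has observed. Intolerance is not one of the stated model terms, and a patient removed before week 8 has only a baseline outcome. The plan does not state the missing-data assumption, includes no sensitivity analysis for departures from it, and does not say whether measurements taken after stopping drug are analysed.

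**Working it through.** **Setting the passages side by side.** Take two hypothetical patients who stop drug for intolerance and still consent.

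| Rule followed | Stops before week 8 | Stops between weeks 8 and 16 |
|---|---|---|
| Section 1 (withdrawn from the study) | Week 0 only; 2 of 3 outcome visits lost | Weeks 0 and 8; 1 of 3 lost |
| Discontinuation section, follow-up read as outcome visits plus call | Weeks 0, 8 and 16; none lost | Weeks 0, 8 and 16; none lost |
| Discontinuation section, follow-up read as safety call only | Week 0 plus call; 2 of 3 lost | Weeks 0 and 8 plus call; 1 of 3 lost |

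The Synopsis gives the first row when the investigator so decides. Intolerance is not among the exceptions in the discontinuation section, so the first row disagrees with that section on either reading of its follow-up. The wider reading is not assured: the Section 6 schedule labels week 8 as during treatment and week 16 as end of treatment, and only the week 20 call as follow-up. On the narrower reading, no passage requires an outcome visit after drug is stopped.

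**The plan's own attrition figures.** The Introduction expects about 20% dropout and 16 retained per group. Inflating, 16 / (1 − 0.20) = 20 per group. This matches the Synopsis, where the number requested "is 20 subjects per group or 40 subjects total". Expected loss is 40 × 0.20 = 8 patients, leaving 32. Section 7 uses 25% in its own calculation; applied to 40, that leaves 40 × 0.75 = 30. Neither figure is split by reason or by arm, so the share due to intolerance is unknown.

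**Whether a bias can be derived.** If withdrawn patients contributed nothing, the shift in an arm's mean would be (fraction withdrawn) × (gap between withdrawn and remaining patients). Both inputs are assumptions:

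- 2 of 20 withdrawn, gap 0.5 SD: 0.10 × 0.5 = 0.05 SD.
- 3 of 20 withdrawn, gap 1.0 SD: 0.15 × 1.0 = 0.15 SD.

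The formula also ignores the week 8 value of anyone who stops later, which the mixed model would use. It shows how the quantities combine and is not an estimate for this trial.

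**Whether a power loss can be derived.** The Synopsis reports 73% power but gives no effect size, SD or sample size for that figure. Back-solving a two-sided two-sample t-test at 0.05 gives d of about 0.94 if 73% refers to 16 per group, or about 0.83 if it refers to 20. Taking d = 0.94 as an assumption:

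| Active vs placebo measured | Power |
|---|---|
| 20 vs 20 | 83% |
| 18 vs 20 | 80% |
| 17 vs 20 | 79% |
| 16 vs 16 | 73% |
| 14 vs 16 | 70% |
| 13 vs 16 | 68% |

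Losing 2 or 3 active patients gives 79–80% if they are the only losses, and 68–70% if they come on top of the planned dropout. The documents do not say which applies.

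**The case against.** The strongest reply is that there is little real conflict. Section 1 is a one-line summary that may use withdrawal loosely for stopping treatment. The discontinuation section is the dedicated text, and it mixes the two ideas itself by making continued study participation the test for stopping drug. If its follow-up means only the 30-day call, a patient who leaves under Section 1 and takes the call could be said to satisfy both.

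Part of this stands. The discontinuation section cannot be cited as already guaranteeing week 8 and 16 data, because it does not name the procedures it means. But the Synopsis repeats the study-level wording, so Section 1 is not an isolated slip, and on the narrow reading the later outcomes are simply not required.

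Two stronger readings are tempting and are not supported:

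- **That losses would fall mainly on canagliflozin.** A reader might infer this from the adverse events of special interest in Section 5, such as genital and urinary infections and volume-related events. That list names events under monitoring and gives no rates by arm and no discontinuation rates. Unequal loss is possible but not shown.
- **That a definite bias or fall in power follows.** Every such figure needs assumed inputs, and patients who stop after week 8 still contribute two measurements.

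**Conclusion.** The inconsistency is in the current text and should be resolved. Under Section 1 as written, an intolerant patient loses one or two of the three outcome visits for a reason tied to treatment; under the discontinuation section that patient stays in follow-up of unstated content. The mixed model alone does not settle the matter, because the plan claims only efficiency for it and does not address missingness related to treatment.

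The size cannot be derived from the documents. What is known is that 40 patients are randomised and 8 are expected to be lost at the plan's 20%, with no breakdown by cause or arm. The conclusion rests on the wording of the passages and not on the illustrative bias or power figures. It implies no view on when treatment should be stopped.

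**What to change.** Reconcile the Synopsis (Criteria for Evaluation), Section 1, the discontinuation section and Section 5 (Pregnancy) so that stopping study drug is distinguished from ending outcome data collection. In particular:

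1. Define the follow-up procedures that apply after discontinuation, saying explicitly whether the week 8 and 16 outcome visits are included.
2. State that patients who stop drug but still consent, and whom no other protocol rule withdraws from the study, are invited to the remaining week 8 and 16 outcome visits.
3. State in Data Analysis that these patients are analysed as randomised, with their measurements after stopping drug included.

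The qualification in item 2 is needed. A rule that only consent-related reasons end data collection would clash with the pregnancy text. When treatment stops remains a clinical matter for the protocol team, and patients remain free to decline visits.

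The cost is a few sentences; the visits are already in the Section 6 schedule. The downside is that outcomes measured off drug may dilute the estimated on-drug effect, so the plan should say that its comparison is of the groups as randomised, whether or not drug was continued.

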# 2 STUDY OBJECTIVES

## PRIMARY OBJECTIVE

**To determine whether 4 months of Canagliflozin modifies CD34+ cell number, gene expression and migration function.**

## PROTOCOL FOR OBTAINING CD34+ CELLS:

We will obtain a total of approximately 95 mL of peripheral blood per visit. Of these 95 mL, 60-70 mL will be used to obtain CD34+ cells from mononuclear cell (MNC) population and 25-35 mL for biochemistry and plasma ELISA assays. MNC will be obtained from whole blood similar to protocols described before. MNCs will be put through CD34 magnetic bead column to obtain CD34+ cells (Miltenyi Biotec). Purity of CD34+ cells, post sort, usually is above 90%, to be verified by FACS analysis.

- A. From Mononuclear (MNC) population (pre CD34+ magnetic column sorting): We will assess the proportion of various cell types, progenitor stems and mature cells in MNCs to note if Cana influences stem vs non stem cell pool such as percentage of : CD34, CD309 (VEGFR2-KDR), CD184 (CXCR4), receptor substrate for SDF1 alpha, CD31 (PECAM-1, a mature circulating endothelial cell marker), CD133 (a progenitor marker), CD144 (Vascular Endothelial cadherin), Sytox Blue OR Propidium Iodide staining (to detect apoptotic cells).
- B. MNC cells (prior to CD34 magnetic bead sorting) will be also used to assay CFU Hill Colony forming unit (Stem Cell Technologies- Cat#05900) media for Colony Forming unit (CFU) Assay. CFU will be counted on 5-7 days post plating (from initial plating).
- C. From CD 34+ cell population (Post Sorting):
  - a. Migration Assay using SDF1Alpha concentrations of 0, 10, 100ng/ml and VEGF-A concentrations of 20 and 50 ng/ml, using 150,000 cells in 300ul serum free cell suspension media per insert.
  - b. Gene expression studies. Genes to be assessed on sorted CD34 positive cells:

- i. Endothelial lineage cell surface markers: CD34, VEGFR2 (KDR), CD31, CD144
- ii. For Anti-oxidant gene expression: Superoxide dismutase (SOD) 1, 2 and 3, catalase, glutathione- peroxidase.
- iii. Apoptosis pathway: p53, p21, Bcl2, caspase-3
- iv. Endothelial Function Assay Gene: endothelial Nitric Oxide Synthase, von-Willebrand's Factor
- v. Genes associated with progenitor cell chemotaxis: VEGF-A, SDF1 alpha, CXCR4.

## **SECONDARY OBJECTIVE**

**To determine whether use of Canagliflozin alters other cardio-metabolic health indicator parameters such as: arterial stiffness measures, resting metabolic rate, body composition measures, hs-CRP, IL-6, TNF-alpha (inflammatory markers), fasting lipid profile, levels of insulin, glucose appetite controlling hormones and urine levels of microalbumin (Microalbumin/Creatinine ratio).**

We expect to corroborate our findings of the Primary Objective (cellular outcome measures) with traditional markers of endothelial/ vascular function such as serum biochemistry and arterial stiffness.

### **Effect of Cana on Serum Biochemistry:**

While we believe cell based biomarkers are superior to traditional serum biomarkers, we believe the outcome report will be stronger if one can show positive co-relation between the two outcome measures. We therefore will be looking at:

- I. Inflammation, apoptosis and anti-oxidant protein levels: Highly selective C-reactive protein (hs-CRP), IL-6, TNF-alpha, fasting glucose, insulin and lipid profile.
  - a. Glycemic control will be evaluated by measuring fasting blood glucose, insulin levels and HbA1c. Fasting blood glucose, insulin and lipid profile will be used to assess insulin resistance (32, 37)
- II. Plasma SDF1 alpha (ELISA) and GLP-1 (ELISA) will be estimated to assess endothelial health and factors that may influence CD34+ cell chemotaxis
- III. Estimation of Creatinine Clearance and proteinuria: 24hr urinary protein estimation and creatinine clearance (obtained via micro-albumin/creatinine ratio from a spot urine sample).
  - a. *Subjects will have the option of opting into a sub-study that is being run by [name] at the Veterans Affairs (VA) Maryland Health Care System. 10-20 mL of the excess fresh spot urine that has been collected would be sent to the VA for exosome analysis. This is optional, and is not required of subjects. For details of urine-exosome study please see page 31.*
- IV. The glomerular filtration rate (GFR) will be estimated using the CKD-EPI (Chronic Kidney Disease Epidemiology Collaboration) equation. The CKD-EPI equation, expressed as a single equation, is:
  - a.  $GFR = 141 \times \min(Scr/\kappa, 1)^a \times \max(Scr/\kappa, 1)^{-1.209} \times 0.993^{Age} \times 1.018$  [if female]  $\times 1.159$  [if black]; where Scr is serum creatinine (mg/dL),  $\kappa$  is 0.7 for females and

0.9 for males,  $\alpha$  is  $-0.329$  for females and  $-0.411$  for males, min indicates the minimum of  $Scr/\kappa$  or 1, and max indicates the maximum of  $Scr/\kappa$  or 1.

### **Effect of Cana on Body Habitus (Determination of body composition and visceral fat) AND Resting Metabolic Rate.**

As we plan to study cardio-metabolic effect of Cana we believe the RMR and body composition data is useful.

- I. Using body composition scale:
  - a. Height and weight will be measured and the body mass index ( $BMI=kg\cdot m^{-2}$ ) used as an indicator of relative weight.
  - b. The body composition scale calculates body fat%, total body water%, fat free mass, etc. in addition to BMI.
- II. Resting Metabolic Rate (RMR): at weeks 0, 8 and 16 of the protocol using ReeVue (trademark) machine, with or without SGLT2 inhibitor therapy to ascertain if Cana has any effect on RMR. Other related trials have shown weight loss but effect on metabolic rate has not been studied.

[figure not shown]
### **Effect of Cana on Assays of Arterial Stiffness:**

- I. We will acquire Pulse Wave Analysis and Vascular Flow using SphygmoCor CP system from ATCOR as a measure of central arterial pressure and arterial stiffness. Again SGLT2 inhibitors have been shown to reduce systolic blood pressure but effect on stiffness has not been looked at, except with Empagliflozin
- II. Vessel health will be assessed by degree of arterial stiffness, using arterial tonometry.
- III. The central and the aortic pressure is assessed by pulse wave analysis (PWA) and pulse wave velocity (PWV).
- IV. Arterial stiffness will be assessed using Vascular Flow and wave form analysis equipment, SphygmoCor CP system from ATCOR^19.

## **3 INVESTIGATIONAL PLAN**

### **STUDY DESIGN AND DURATION**

#### **40 Type 2 diabetic Subjects Aged 30-70 on stable dose of certain anti-diabetic therapies**

**+/- 6 day window for visits**

\*Assessed at week 0, 8 and 16: Biochemical and cellular markers of endothelial function and Pulse wave analysis and velocity (PWA and PWV), REE and Adiposity.

Week 20 - A telephone call to subjects will be made 30 days after last dose of study medication to determine if there have been any adverse events.

**AVAILABLE RELATED STUDIES AND EXPECTED RESULTS:**

Studies measuring changes to EPCs in type 2 diabetes patients are very limited.

Use of CD34 positive cells as a cardiovascular risk surrogate has been reported in the past. Various studies, have shown that various disease states, including those seen in diabetes, can deplete and damage EPC, thereby diminishing their regenerative potential. The inability to maintain or repair damaged endothelial tissue leads to cumulative vascular dysfunction and cardiovascular disease.

*We hypothesize that monitoring number, function and gene expression of endothelial progenitors will allow us to quantify cardiovascular disease risk at the onset and regenerative potential post intervention at a cellular level. It will also help us to identify and correlate the best endothelial function bio-chemical inflammatory marker as an early indicator of cardiovascular disease progression in early type 2 diabetes and identify patients that are responders.*

Cana can influence the glucose transportation and modify intercellular glucose and cell energetics, and so it can influence the migration of the cell. SDF-1alpha, being a chemotactic agent, will also influence migration depending on its level.

Cana 100 mg or placebo will be added to patients who have type 2 diabetes with HbA1C of 7.0 to 10 % (both inclusive) while being on any combination of the following anti-diabetic therapies:

metformin (1-2 grams), insulin, GLP-1 agonists, a DPP-IV inhibitor, or sulfonylureas. As per ADA, Metformin is the 1st line of care along with life-style modification. While Metformin on its own may affect inflammatory biomarkers, the effect is minimal at best, particularly in presence of endothelial dysfunction. Also both the placebo and Canagliflozin group will be on any combination of the following anti-diabetic therapies: metformin (1-2 grams), insulin, GLP-1 agonists, a DPP-IV inhibitor, or sulfonylureas. Our study population will include equal numbers of adult male and female Type 2 diabetes (T2DM) patients aged 30-70 years, enrolled in both arms of the study.

Patients will be treated with 100 mg of Cana or placebo for 16 weeks. This time interval has been previously shown to be adequate to observe changes to Endothelial Progenitor Cells (EPCs).

